14.0 RECORD KEEPING/REPORTING

14.1 Data Collection

The study will create 21 CFR Part 11 compliant data flows for relevant study sources to 21 CFR Part 11 compliant servers housing information on participant demographics, baseline health history, questionnaires, data from the Irregular Rhythm Notification features and ECG app, ambulatory ECG monitor results, Adverse Events, and 15- and 60-day PROs.

14.2 Study Documentation

Study documentation includes but is not limited to all consent forms, app screens, app based forms, Irregular Rhythm Notification data, ECG app data, PROs, ambulatory ECG monitor reports, and regulatory documents (e.g., signed protocol and amendments, IRB correspondence and approval, approved and signed participant consent forms, Statement of Investigator form, etc.). The investigator will prepare and maintain complete and accurate study documentation in compliance with applicable federal, state, and local laws, rules, and regulations.

This document contains information that is privileged or confidential and may not be disclosed unless such disclosure is required by applicable laws and regulations. The information in this document is the property of Apple Inc. and may not be reproduced, published, or disclosed to others without written authorization from Apple Inc.

Abbreviation or special term	Explanation
AE	Adverse Event
AF	Atrial Fibrillation and Atrial Flutter
AFib	Atrial Fibrillation
Apple Watch ECG app-AFib	Apple Watch ECG app classification of atrial fibrillation
CI	Confidence Interval
EAS	ePatch Analysis Set
EEAS	ePatch Eligibility Analysis Set
ECG	Electrocardiography, Electrocardiogram, Electrocardiographic
FAS	Full Analysis Set
FOG	Fallout Subgroup
IRN	Irregular Rhythm Notification
IPNA	Irregular Pulse Watch Notification Algorithm
PAC	Premature Atrial Contractions
PPG	Photoplethysmography, Photoplethysmogram
PRO	Patient Reported Outcome
PVC	Premature Ventricular Contractions
SAE	Serious Adverse Event
SAP	Statistical Analysis Plan
SV1	Study Visit 1
SV2	Study Visit 2

Revision history

Revision	Date	Section/Page	Changes Made -- Reasons for the Change

INTRODUCTION

This statistical analysis plan (SAP) is a comprehensive and detailed description of the strategy, rationale and statistical techniques that we will use to evaluate the ability of the Apple Watch Irregular Pulse Watch Notification Algorithm (IPNA) feature and Electrocardiography (ECG) app to identify atrial fibrillation or atrial flutter (AF) and facilitate subsequent clinical evaluation among users who contact AppleCare.

1. STUDY DETAILS

1.1 Study objectives

Objective 1a: To measure the proportion of participants with an Irregular Rhythm Notification (IRN) prior to enrollment who have atrial fibrillation or atrial flutter (AF) confirmed by ambulatory electrocardiographic (ECG) patch monitoring.

Objective 1b: To measure the proportion of participants with an ECG app classification of Atrial Fibrillation (ECG app-AFib) prior to enrollment who have AF confirmed by ambulatory ECG patch monitoring.

Objective 2a: To measure the proportion of participants who receive an IRN or ECG app-AFib reporting contact with a non-study healthcare provider at 15 and 60 days after study enrollment.

Objective 2b: To measure the proportion of participants with an ECG app classification of inconclusive prior to enrollment who have AF confirmed by ambulatory ECG patch monitoring.

Objective 2c: To measure the proportion of participants who have AF confirmed by ambulatory ECG patch monitoring by age at enrollment (< 65 and 65+).

1.2 Study design

This will be a prospective, single arm, experimental, non-significant risk study conducted with the assistance of eligible participants wearing an Apple Watch Series 1-4 with the IRN feature or an Apple Watch Series 4 with the ECG app who receive an IRN or an ECG app classification of AF or “inconclusive”.

The Irregular Rhythm Notification (IRN) feature is a software-only mobile medical application that analyzes pulse rate data to identify episodes of irregular heart rhythms suggestive of AFib. Using observable variations in photoplethysmogram (PPG) signal intensity, changes in blood flow can be measured and beat-to-beat pulse measurements can be made. During normal sinus rhythm, there is minimal variation in pulse. However, during AF, the beat-to-beat variability increases significantly. Therefore, a PPG signal can be used to differentiate between a regular pulse and an irregular pulse that may be indicative of AF.

An algorithm has been developed by Apple to identify periods of irregular pulse based on PPG signal variation as measured by the Irregular Pulse Notification Algorithm (IPNA). The time between PPG signal peaks observed during periods of minimal arm movement are marked as intervals between heart beats. A tachogram is a period of time over which heart beat intervals are measured. The degree of beat-to-beat variability is measured from spot tachograms over the course of approximately one minute intervals. An irregular tachogram is flagged when the variability, measured using a Poincare plot, crosses a predefined threshold. An IPNA checks multiple tachograms over a period of approximately an hour or more. An IRN is then sent to the user when a period of an irregular pulse suggestive of AFib has been identified.

The ECG app is a software-only mobile medical application intended for use with the Apple Watch to create, record, store, transfer, and display a single channel ECG similar to a Lead I ECG. The ECG app processes electrical signals from two sensors on the Apple Watch - an electrode on the back of Apple Watch and an electrode on the digital crown. A user opens the ECG app on their Apple Watch, places a finger on the digital crown, and remains still for 30 seconds to capture an ECG. The ECG app analyzes the waveform to determine the presence of atrial fibrillation (AF) or sinus rhythm on a classifiable waveform. The ECG app waveform is stored in the Health App and can be exported as a .pdf. The ECG app provides rhythm classifications such as AF, “Inconclusive”, “Heart Rate Over 120”, or “Heart Rate Under 50”. The ECG app group classifications; “Inconclusive”, “Heart Rate Over 120”, or “Heart Rate Under 50” are all considered inconclusive for the purposes of this study and are considered eligible for this study. Both the IRN feature and the ECG app were granted United States Food and Drug Administration (FDA) de novo classification on 9/11/2018.

Participants who call into AppleCare and self-report having received an IRN or ECG app classification of AF or inconclusive will be offered information about participation in the study. The AppleCare representative will offer to e-mail the participant a link to download the Study App for more information. If the participant agrees, the participant will be emailed a link to download the Study App. Once downloaded, the Study App will provide the information about the study and screen for eligibility. If the participant meets the eligibility criteria and wishes to enroll in the study, the Study App will initiate the consenting process and provide the consent and authorization to sign in the app. Participants who install the Apple Heart Study 1.2 App and meet the eligibility criteria proceed to consent and then enroll in the study. Participants will be required to provide signed informed consent; once enrolled they will complete a short questionnaire to collect demographic information, medical history, and health status, after which the study period will commence.

After enrollment, participants will be prompted to contact the Study Telehealth Provider to conduct Study Visit #1 (SV1) via voice or video. During SV1, participants will undergo a virtual medical evaluation which will include an abbreviated assessment for symptoms, medical history, and medications. Participants with urgent symptoms (chest pain, shortness of breath, fainting/losing consciousness) will be directed to an urgent care clinic or emergency room for medical evaluation. For participants with non-urgent symptoms, the Study Telehealth Provider will order an ambulatory ECG monitor (i.e., an ePatch) from

BioTelemetry. Participants will be expected to contact the Study Telehealth Provider within 30 days of enrollment. Study participants will receive reminders via email and phone calls if needed to initiate SV1. Participants who call after 30 days will still be able to obtain an ePatch and undergo remaining study procedures, but may not be included in all analyses.

[figure not shown]
Participants will be mailed the ePatch, and once received, the participant will be required to wear it for up to 7 days. The minimum analyzable time acceptable for primary analysis is one hour. Participants with the ECG app will be asked to take an ECG app recording at least twice daily while wearing the ePatch, as well as after receiving an irregular rhythm notification. The participant will then mail the ambulatory ECG monitor back to BioTelemetry within 45 days of enrollment, which will generate a standard technical report that will be read by BioTelemetry's technical readers. The report will be adjudicated by two board-certified clinicians, and a final report will be made available to the Study Telehealth Provider by BioTelemetry.

After the final ambulatory ECG monitor report is made available to the Study Telehealth Provider, the Study Telehealth Provider will contact the participant to prompt them to complete Study Visit #2 (SV2). During SV2 the ePatch results will be reviewed. If AF or any other arrhythmias have been detected in reviewing the ambulatory ECG monitor data, or if there are other non-urgent symptoms needing further evaluation, the Study Telehealth Provider will direct the participant to their primary health care provider, or other health care provider as deemed appropriate. The report and visit summary will be made available to the participant and also to the participant's physician or health care provider, if the participant provides his/her physician information and permission to send that physician a copy of the report. For participants who do not have an established primary health care provider, the Study Telehealth Provider will encourage and offer advice in establishing a primary care provider per standard Study Telehealth Provider protocol.

1.3 Number of Participants Needed to Address Objectives

This clinical study is not designed to test any pre-specified statistical hypotheses. Because all participants enrolling in this clinical trial will either have received an IRN or an ECG app-AFib classification, we derived the number of enrolled participants needed to achieve our desired precision for addressing Objectives 1a and 1b.

To obtain a 95% confidence interval (CI) with a width no greater than 0.10 when addressing Objective 1a we will require 400 IRN participants that are exclusively in the IRN group (i.e., who do not enter the study via the ECG app), who are deemed eligible for ePatch receipt and who return their ePatches. Similarly, for Objective 1b to obtain a 95% CI with a width no greater than 0.10 we will require 400 participants who exclusively enroll via the ECG-app classification of AFib, who are deemed eligible for ePatch receipt and who return their ePatches.

The figure above displays the 95% CI width for the target sample size of 400 (over the range of possible AF percents we could observe) and three sample sizes that represent a failure to meet the target; n=350 (87.5% of target), n=300 (75% of target) and n=200 (50% of target). The height of the lines (the vertical axis) correspond to the CI width. The horizontal axis corresponds to the percent AF observed. As noted 400 patches (the blue line) will ensure the estimated CIs are no wider than 10%. The lines representing a failure to meet the target number of returned ePatches for each group shows at worst the CI could be as wide as 13.9% at 50% of the target and a percent with AF of 50%. However, even at 87.5% or even 75% of the recruitment target the worst case is a CI width of 11.3% and in both cases a modest amount of possible AF percentages will yield a CI with a width < 10%.

If, after enrolling 500 participants, we observe that there is 50% overlap or greater between participants who enroll through both the IRN and the ECG app, we will modify our targeted enrollment with the understanding that the reporting of findings will be accompanied with a detailed context of the types of subjects that contribute to both estimates addressing Objectives 1a and 1b.

Allowing for an approximate attrition rate of 35% and an overlap of 50% between participant types (IRN vs ECG-app) we calculated a minimum target enrollment of 2600 participants.

Further, the expected period for completion of study recruitment is approximately 6 months. If, 60 days after the study opens, there is evidence that enrollment rates will not be adequate to meet enrollment goals for each subgroup, then alternative recruitment strategies will be employed to help reach recruitment goals.

2. ENDPOINTS

2.1 Primary Endpoints

The primary endpoint of the study is

- An indicator for whether atrial fibrillation or atrial flutter of at least 30 seconds duration on an ambulatory ECG patch monitor.

2.2 Secondary Endpoints

The secondary endpoints are

- Arrhythmias other than AF on an ambulatory ECG patch monitor.
- Self-reported contact with healthcare provider.

3. ANALYSIS SETS

The Full Analysis Set (FAS) will consist of all enrolled participants who complete the informed consent process. This analysis set will be used to summarize subject demographics, medical history, adverse events, self-reported health status, diagnosis, and contact with the health care provider.

The ePatch Eligibility Analysis Set (EEAS) will consist of those in the FAS deemed eligible to receive an ePatch at Study Visit #1. This analysis set will be used to assess Objective 2a.

The ePatch Analysis Set (EAS) will consist of all those in the EEAS who receive and return an ePatch with at least 1 hour of usable data and who do not belong to the Fallout Subgroup. This analysis set will be used to assess Objectives 1a, 1b, and 2b and 2c. We will repeat these analyses in the EEAS as a sensitivity analysis using appropriate methods for handling missing data.

The Fallout Subgroup Analysis Set (FOG) will consist of participants who enroll and complete the informed consent process but otherwise do not complete the study. Reasons for study incompleteness include; failure to contact Study Telehealth Provider within 30 days of enrollment, being deemed ineligible at Study Visit #1 for ePatch wear due to emergent symptoms, ePatch not returned within 45 days of enrollment, failure to start wearing ePatch within 14 days of shipment, unable to verify at Study Visit #1 a study eligible IRN or ECG-app notification, study withdrawal (i.e., withdrawal of consent), or lost to follow-up (i.e., death). We will present demographic and medical history information for this analysis set.

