Participants with urgent symptoms (chest pain, shortness of breath, fainting/losing consciousness) will be directed to an urgent care clinic or emergency room for medical evaluation. For participants with non-urgent symptoms, the Study Telehealth Provider will order an ambulatory ECG monitor (i.e. an ePatch) from BioTelemetry. Participants will be expected to contact the Study Telehealth Provider within 30 days of enrollment. Study participants will be reminded to initiate Study Visit #1 with reminders via email and phone calls if needed. Participants who call after 30 days will still be able to obtain an ePatch and undergo remaining study procedures, but may not be included in all analyses.

The participants will be mailed the ambulatory ECG monitor, which the participant will then be requested to wear for up to 7 days. The minimum analyzable time acceptable for primary

This document contains information that is privileged or confidential and may not be disclosed unless such disclosure is required by applicable laws and regulations. The information in this document is the property of Apple Inc. and may not be reproduced, published, or disclosed to others without written authorization from Apple Inc.

analysis is one hour. Participants with the ECG app will be asked to take an ECG app recording at least 2 times each day while wearing the ePatch, as well as after receiving an irregular rhythm notification. The participant will then mail the ambulatory ECG monitor back to BioTelemetry, which will generate a standard technical report that will be read by BioTelemetry's technical readers. The report will be adjudicated by two board-certified clinicians, and a final report will be made available to the Study Telehealth Provider by BioTelemetry.

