10.0 STATISTICAL CONSIDERATIONS

10.1 Analysis Sets

All analyses will be reported for the overall cohort, as well as by cohort status determined at enrollment: (1) Irregular Rhythm Notification, and status of (2) Afib or (3) Inconclusive via the ECG app (i.e., with at least 1 ECG recorded within the 14 days before study enrollment indicating classification of either AFib or Inconclusive, where the latter is defined as “Inconclusive,” “Heart Rate Over 120,” or “Heart Rate Under 50”).

The Full Analysis Set (FAS) will consist of all enrolled participants who complete the informed consent process. This analysis set will be used to summarize subject demographics, medical history, adverse events, self-reported health status, diagnosis, and contact with the health care provider.

The ePatch eligible analysis set (EEAS) will consist of those in the FAS deemed eligible to receive an ePatch at Study Visit #1.

The ePatch Analysis Set (EAS) will consist of all those in the EEAS who receive and return an ePatch with at least 1 hour of usable data and who do not belong to the Fallout Group.

The Fallout Subgroup Analysis Set (FOG) will consist of participants meeting the criteria of Section 7.10. Demographic and medical history information will be presented for this analysis set.

Objectives 1a, 1b, and 2b and 2c will be conducted using the EAS, whereas Objective 2a will be conducted using the EEAS. The analyses for Objectives 1a, 1b, and 2b and 2c will be repeated in the EEAS as a sensitivity analysis using appropriate methods for handling missing data.

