4.3 Analysis Methods

Analysis of the Primary Endpoint Addressing Objective 1a and 1b

For Objectives 1a and 1b we have designed the study to estimate the proportion of participants diagnosed with AF within a 0.10 confidence interval width.

Objective 1a – The proportion of participants with an IRN prior to enrollment who have AF confirmed by ambulatory ECG patch monitoring.

This proportion will be estimated as the ratio of the number of participants in the EAS who have atrial fibrillation or atrial flutter of at least 30 seconds duration on patch wear and received an IRN before enrollment, divided by the number of participants in the EAS who received an IRN before enrollment. An exact 95% two-sided confidence interval will also be presented. We will also describe the number of participants who received an IRN before or during enrollment with arrhythmias other than atrial fibrillation.

Objective 1b Analysis – The proportion of participants with an ECG app-AFib classification prior to enrollment who have AF confirmed by ambulatory ECG patch monitoring.

This proportion will be estimated as the ratio of the number of participants in the EAS who have atrial fibrillation or atrial flutter of at least 30 seconds duration on patch wear and received an ECG app-AFib classification before enrollment divided by the number of participants in the EAS who received an ECG app-AFib classification before enrollment. An exact 95% two-sided confidence interval will also be presented. We will also describe the number of participants who received an ECG app-Fib before enrollment with arrhythmias other than atrial fibrillation.

Analysis of the Secondary Endpoints Addressing Objectives 2a, 2b and 2c

Objective 2a Analysis - The proportion of participants with an IRN or ECG app-AFib classification reporting contact with a non-study healthcare provider at 15 and 60 days after study enrollment.

This proportion will be estimated as the ratio of the number of participants who received an IRN or ECG app-AFib classification in the EEAS who reported contact with a non-study healthcare provider at 15 (and separately at 60) days after study enrollment divided by the number of participants in the EEAS who received an IRN or ECG app-AFib. An exact 95% two-sided confidence interval will also be presented.

Objective 2b Analysis

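### Objective 2a is estimated only in the patch-eligible set, which leaves people out for reasons linked to seeking care and can be settled after day 15

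*Combined protocol and SAP*

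**What the plan says.** Protocol and SAP agree on the set. Protocol 10.1 has "whereas Objective 2a will be conducted using the EEAS", and SAP section 3 makes the same choice in its entry for the EEAS: "This analysis set will be used to assess Objective 2a". By definition, that set "will consist of those in the FAS deemed eligible to receive an ePatch at Study Visit #1". Protocol 10.3.2 and SAP 4.3 then give the ratio. Its numerator is those who "reported contact with a non-study healthcare provider at 15 (and separately at 60) days after study enrollment". Its denominator is confined to the same set, since the count is "divided by the number of participants in the EEAS who received an IRN or ECG app-AFib".

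Three other parts of the plan bear on this:

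- **Who leaves the EEAS.** Under protocol 4.1, participants with urgent symptoms at Visit 1 "will be directed to an urgent care clinic or emergency room for medical evaluation". Protocol 7.3.2 withholds the ePatch in a medical emergency, and also when no alert can be confirmed. Protocol 7.12 and SAP section 3 list ineligibility for emergent symptoms as a fallout reason.
- **When Visit 1 happens.** "Participants will be expected to contact the Study Telehealth Provider within 30 days of enrollment" (protocol 4.1), but later callers may still get a patch. The EEAS definition sets no time limit.
- **Who gets the PROs.** The protocol synopsis sends both to every participant, counted from enrollment. Protocol 7.8 allows 30 days to answer.

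Contact is also described outside the EEAS. The FAS is used to summarise "self-reported health status, diagnosis, and contact with the health care provider" (SAP section 3). Protocol 10.3.4 looks at 60-day provider engagement in the FAS. SAP 4.3 reports contact rates for fallout-subgroup (FOG) members who completed the PRO.

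**The concern.** The objective is worded for participants who received an IRN or ECG app-AFib, and it does not mention patch eligibility. The outcome comes from a questionnaire, not from the patch. Restricting the estimate to the EEAS adds a condition that the objective does not contain, and part of that condition is tied to the outcome: a person sent to urgent care or an emergency room has been told to do what 2a counts. Someone who skips Visit 1 may have gone to their own doctor, or may have done nothing.

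The day-15 estimate has a further problem. Membership of its denominator depends on a visit that can come after the time point being described.

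At stake is whether the reported proportion describes everyone who was alerted and enrolled, or only those who also reached Visit 1 and were cleared for a patch.

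**Working it through.** The plan states no expected contact rate, referral rate or precision for 2a, so there is no figure of its own to reproduce. The check has two parts.

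**1. Timing, from the documents.** The 15-day PRO opens at day 15 and can be answered until about day 15 + 30 = 45. Visit 1 is expected by day 30, and later calls are accepted. EEAS membership can therefore be fixed 30 - 15 = 15 days after the day-15 time point, or later still. Protocol 7.4.2 expects most participants to have worn and returned the patch about 14-20 days after enrollment. With a full 7-day wear, that puts Visit 1 no later than day 20 - 7 = 13. Late membership should thus affect a minority, and the day-60 estimate hardly at all.

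**2. Size, by illustration.** Every rate here is an assumption. Let *p* be the contact proportion in the EEAS, *u* the share of all participants dropped as urgent referrals, *c_u* their contact proportion, *s* the share with no Visit 1, and *c_s* theirs. People whose alert could not be confirmed are left out of this sketch.

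FAS proportion = (1 - u - s) × p + u × c_u + s × c_s

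*Urgent referrals only* (s = 0, p = 0.40, c_u = 0.95):

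- u = 0.02: 0.98 × 0.40 + 0.02 × 0.95 = 0.411, so the EEAS is 1.1 points too low
- u = 0.05: 0.95 × 0.40 + 0.05 × 0.95 = 0.4275, 2.75 points too low
- u = 0.10: 0.90 × 0.40 + 0.10 × 0.95 = 0.455, 5.5 points too low

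Over the same range of u, the shortfall is 1.5 to 7.5 points if p = 0.20, and 0.7 to 3.5 points if p = 0.60.

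*Adding people with no Visit 1* (u = 0.05, s = 0.20, p = 0.40, c_u = 0.95), FAS = 0.75 × 0.40 + 0.0475 + 0.20 × c_s:

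| c_s | FAS proportion | EEAS is |
|---|---|---|
| 0.60 | 0.4675 | 6.75 points too low |
| 0.40 | 0.4275 | 2.75 points too low |
| 0.20 | 0.3875 | 1.25 points too high |
| 0 | 0.3475 | 5.25 points too high |

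The sign changes at c_s = 0.40 - 0.0275/0.20 = 0.2625.

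For scale, an exact 95% interval at 40% has a half-width of about 2.4 points with n = 1690 (2600 × 0.65, taking the planned 35% attrition). That n is only a yardstick: people with an inconclusive result alone are not in the 2a denominator, so the real interval would be wider.

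**Coverage of 2a by the plan's safeguards.** The repeat in a wider set (protocol 10.1, SAP section 3) and the anticipated biases introduced in SAP 4.7 name Objectives 1a, 1b, 2b and 2c. Neither names 2a. Imputation within the EEAS (SAP 4.6) cannot bring back people who are outside it.

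**The case against.** The strongest defence is that Visit 1 does more than decide on a patch: it is where the alert is confirmed. Entry is by self-report, the baseline item on notifications allows an unsure answer (SAP 4.2, Table 2), and Phase 1 collects no HealthKit or Watch data (protocol 7.9). A reader might infer that patch eligibility has nothing to do with 2a. The documents do not support that, because the EEAS removes alerts that nobody could confirm and a FAS denominator would let them in. This part of the objection stands and shapes the fix.

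A reader might also infer that the EEAS estimate is biased downwards overall. The urgent-referral component does point that way, but being directed to care is not recorded contact, and the 95% is assumed. The group with no Visit 1 can reverse the sign. With 35% contact in the EEAS, 5% urgent referrals at 95%, and 25% with no Visit 1 and no contact, the FAS value is 0.70 × 0.35 + 0.05 × 0.95 + 0 = 29.3%, below the EEAS value.

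Nor should large shifts be treated as typical. Assuming 10% referred and 25% without Visit 1 would use up the whole 35% attrition allowance before a single patch goes unreturned.

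Finally, the excluded people are not invisible. The FOG includes both those ineligible for emergent symptoms and those who did not call within 30 days, and its contact rates will be reported. That stands as partial mitigation. But the FOG rates cover PRO completers only, the FAS summary has no stated formula, interval or restriction to IRN and ECG app-AFib, and the FAS engagement analysis in protocol 10.3.4 concerns day 60.

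**Conclusion.** The concern holds in a limited form. The only specified estimate of 2a is in a set narrower than the objective, with selection partly linked to the outcome and, for a minority, decided after day 15. The urgent-referral part plausibly costs about 1 to 5.5 points at an assumed 40% contact. This can exceed the illustrative 2.4-point half-width, but it rests wholly on assumed rates. The net direction is unknown.

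Objective 2a is secondary and descriptive, with no hypothesis test, and the primary objectives are untouched. It would be wrong to read this as a flaw in the study's main result. It is a worthwhile and inexpensive improvement, because no planned 2a analysis would show how far the selection matters.

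**What to change.** - In protocol 10.1 and 10.3.2 and SAP 3 and 4.3, estimate 2a at days 15 and 60, each with a 95% confidence interval, in FAS members who self-reported an IRN or ECG app-AFib at enrollment. Handle missing PROs as in SAP 4.6.
- Report the EEAS estimate beside it, and a further version that excludes those whose alert could not be confirmed at Visit 1.
- Add 2a to the biases in SAP 4.7.
- Reconcile the urgent symptoms that lead to referral (protocol 4.1, SAP 1.2) with the medical emergency for which the patch is withheld (protocol 7.3.2), so that EEAS membership is clear.

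The cost is wording and a few extra table rows. The PROs already go to everyone, so no new data are needed. The downside is probably more PRO non-response among people without Visit 1, hence heavier reliance on imputation, and some unconfirmed alerts in the FAS denominator. The side-by-side estimates make both visible.
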